### **11.2.3 Additional Data Collected**

Other data collected are as follows:

- Demographics and other baseline characteristics, including height and weight;

- Injection technique, location, and depth;
- Relevant medical history/concomitant diseases;

- Concomitant therapies; and
- Vital signs.

[REDACTED]

#### 11.2.3.1 *Laboratory Assessments*

Non-fasting clinical laboratory tests will be performed at screening (V1) and Week 24 after last injection. These lab tests include clinical chemistry, hematology, and urinalysis to rule out underlying disease that may exclude the subject from participation or require initiation of medical care during the trial [REDACTED].

[REDACTED]

[REDACTED]

#### **11.2.3.2 Vital Signs**

Vital signs will be measured on subjects after they have been seated for approximately five minutes. Resting heart rate and blood pressure (systolic and diastolic, preferably on the same arm each time) will be measured at screening (V1) and Week 24 after last injection.

#### **11.2.4 Appropriateness of Assessments**

Appropriateness of the selected trial assessments is detailed in the respective Effectiveness Assessments ([Section 11.2.1](#)) and Safety Assessments ([Section 11.2.2](#)).

## 12 SAFETY DEFINITIONS AND REPORTING REQUIREMENTS

### 12.1 Definition of an Adverse Event (AE)

An AE is any untoward medical occurrence, unintended disease or injury, or untoward clinical sign (including an abnormal laboratory finding) in subjects, users, or other persons, whether or not related to the Investigational medical device (IMD).

Note:

1. This definition includes events related to the IMD or the comparator.
2. This definition includes events related to the procedures involved.
3. For users or other persons, this definition is restricted to events related to the IMD.

#### 12.1.1 Details of an AE

The period of observation for an AE extends from when the ICF is signed until the subject's last trial visit. Any medical occurrence between the time the ICF is signed and the first treatment with the IMD is an AE and has to be documented in the subject's file and on the AE eCRF page. Any observed AE will be fully investigated, documented, and followed until the event is either resolved or adequately explained, until the EOT visit. In cases of surgical or diagnostic procedures, the condition/illness leading to such a procedure is considered the AE rather than the procedure itself. New AEs reported to the investigator during the observational period, after the last treatment with the IMD, must be documented, treated, and followed like all other AEs.

Treatment-emergent AEs (TEAEs) are defined as AEs with onset at or after the first administration of trial treatment. If an AE starts prior to treatment but worsens at or after treatment, the investigator records this observation as a new AE with onset = time of worsening, t = time of worsening.

A pre-existing condition noted in the medical history should not be reported as an AE, unless the condition worsens or the disease reoccurs during the reporting period. To determine whether a condition has worsened, it is compared to the subject's condition at screening.

Elective treatments planned before screening, and which are documented in the subject's source data, are usually not regarded as AEs. However, elective procedures should be postponed, if possible, until the subject completes their participation in the trial.

#### 12.1.2 Reporting and Handling of an AE

Data pertaining to AEs will be collecte

. The investigator will assess and

record any AE in detail in the subject's file and on the AE eCRF. The following information must be recorded:

- AE diagnosis or main symptom;
- AE localization (restricted to treatment area, systemic). If a local reaction, the corresponding area should be reported;
- Date of onset;
- Intensity (maximum observed using the Severity Grading scale; [Section 12.1.3](#));
- Causal relationship (not related, related) to investigational device and study procedure;
- Causal relationship (not related, related) to comparator device;
- Serious (yes, no), date serious since, and reason for seriousness;
- Outcome ([Section 12.1.5](#));
- AE leading to discontinuation of the clinical trial (yes, no);
- Action taken with medical device;
- Action taken related to the AE; and
- Stop date.

In cases of an SAE (defined in [Section 12.2](#)), the investigator must also complete an SAE Report Form and report it to the sponsor and CRO immediately as described in [Section 12.2.2](#).

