## **7.2.2 Safety Endpoints**

### **7.2.2.1 Secondary Safety Endpoint**

- Incidence of treatment-emergent AEs (TEAEs) related to Radiesse, as reported by the treating investigator throughout the trial.

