### **12.1.4 Causal Relationship of an AE with an Investigational Medical Device**

An AE is considered to be "related" to IMD or to the treatment procedure if a causal relationship between the IMD or the treatment procedure and an AE is at least reasonably

possible (i.e., the relationship cannot be ruled out). In this case, the non-serious event is considered an “adverse device effect” (Section 12.3). If the event is serious, it is a “serious adverse device effect” (Section 12.4).

The expression “reasonable causal relationship” is meant to convey that there are facts (evidence) or arguments to suggest a causal relationship. Otherwise, the relationship should be considered as “not related”.

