### 12.3 Definition of an Adverse Device Effect (ADE)

An ADE is defined as an adverse event related to the use of an IMD.

Note:

1. This definition includes AEs resulting from insufficient or inadequate instructions for use, deployment, implantation, installation, or operation or any malfunction of the IMD.

2. This definition includes any event resulting from use error or from intentional misuse of the IMD.

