#### **13.4.2.1 Secondary Safety Endpoints**

Incidences of TEAEs related to Radiesse will be calculated at the SOC level and at the PT level and will be presented by treatment (where applicable) and overall.

[figure not shown]

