6.2 Safety Endpoints

[figure not shown]
Safety endpoints are defined in [Section 5.2](#). Safety analyses will be analyzed for the SES if not stated otherwise.

AEs will be coded according to the Medical Dictionary for Regulatory Activities (MedDRA) version that is in effect at the time the database is closed.

Only TEAEs will be analyzed. Non-TEAEs will be listed only. For definitions of TEAEs and non-TEAEs see [Section 5.2](#).

The investigator will report for each TEAE whether only the right NLF, only the left NLF, or both NLFs were affected or whether the treatment area was not affected.

Incidences of TEAEs will be presented in frequency tables. TEAEs affecting the treatment area (either or both NLF) will be analyzed by actual treatment of the respective NLF. Further, incidences of TEAE not affecting the treatment area (i.e. not affecting any NLF) and incidences of TEAEs in total will be presented. The total column will not only include TEAEs affecting either or both treatment NLFs but also TEAEs not affecting the treatment area.

Listings and, if applicable, tables displaying incidences for TEAEs leading to discontinuation, TESAEs, and deaths will also be provided.

[figure not shown]
Further details on analyses of TEAEs are presented in [Section 6.2.1](#) and [Section 6.2.3](#). [REDACTED]

[figure not shown]

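### Does listing the study procedure with the investigational device in one causality item distort the count of Radiesse-related events?

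*Protocol*

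**What the plan says.** Protocol 12.1.2 lists what the investigator records for each adverse event. Two of its bullets concern causality: "Causal relationship (not related, related) to investigational device and study procedure" and "Causal relationship (not related, related) to comparator device". The procedure is named in the first and not in the second.

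Protocol 12.1.4 calls an event related if "a causal relationship between the IMD or the treatment procedure and an AE is at least reasonably" possible, and classes such an event, when non-serious, as an adverse device effect. Protocol 12.3 is narrower: "An ADE is defined as an adverse event related to the use of an IMD".

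The secondary safety endpoint in Protocol 7.2.2.1 is "Incidence of treatment-emergent AEs (TEAEs) related to Radiesse, as reported by the treating investigator throughout the trial". Protocol 13.4.2.1 tabulates it by system organ class and "at the PT level and will be presented by treatment (where applicable) and overall". SAP 6.2.2 takes its columns from SAP 6.2. There the investigator states for each event whether the left NLF, the right NLF, both or neither was affected, and "TEAEs affecting the treatment area (either or both NLF) will be analyzed by actual treatment of the respective NLF". Events outside the treatment area are shown as well. On the last column, SAP 6.2 says: "The total column will not only include TEAEs affecting either or both treatment NLFs but also TEAEs not affecting the treatment area".

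**The concern.** In a split-face trial nobody receives Radiesse alone, so each event has to be attributed to one product, to the other, or to the act of injecting. Attaching the procedure to the Radiesse item only looks lopsided. Suppose the case report form has one yes/no answer for device and procedure together. An injection bruise on the Restylane NLF, or a procedure-related event away from both NLFs, would then be answered as related, and that answer would be the only available flag for relatedness to Radiesse.

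The table of Radiesse-related events could then hold events that Radiesse did not cause, and related-event counts for the two products would rest on unlike questions. This is the only safety endpoint named in the public text, and Protocol 8.2 says the trial compares the safety profiles of both products. Injection-site reactions are expected after either product (after-injection sections under Protocol 10.5.1.2), so the affected events would not be rare curiosities.

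**Working it through.** **1. One field or two?** The documents do not include the case report form, so the reading rests on the wording.

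- The list in 12.1.2 describes content. Its seriousness bullet asks for a yes/no answer, a date and a reason, which are three data items. Its localization bullet asks for local or systemic and, if local, the area. One bullet therefore does not imply one field.
- Protocol 12.1.4 joins device and procedure with *or*, which fits two separate assessments.
- The notes to Protocol 12.1 mention the two devices in one note and the procedures in another.

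On the two-field reading the form holds Radiesse, procedure and Restylane as three items, and SAP 6.2 adds the affected side. That is all the information needed to separate device from procedure.

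**2. Follow one event on the one-field reading.** Take a needle bruise confined to the Restylane NLF and answered as related on the combined item.

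| Column of the Radiesse-related table | Does the bruise enter? | Reason |
|---|---|---|
| Radiesse | No | SAP 6.2 assigns by actual treatment of the affected NLF |
| Restylane | Yes | same rule |
| Outside the treatment area | No | an NLF is affected |
| Total | Yes | covers both NLFs and everything else |

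A procedure-related event away from both NLFs would enter the outside-area and total columns. The Radiesse column is protected from Restylane-side events whatever the form looks like. Misplaced local events are visible in the Restylane column beside it.

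**3. Size of the total-column effect.** The documents give no event rates, so there is no planned figure to reproduce on this point. The one input from the plan is about 118 randomized subjects (Protocol 9.1), taken here as all treated. The rest are assumptions:

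- q: probability of a procedure-type event on each NLF, with every Radiesse-side event flagged;
- f: share of Restylane-side events answered as related on the combined item;
- phi: correlation between the two sides of one face.

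The probability of an event on the Restylane side only is q(1−q)(1−phi), so

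Total = q + f·q(1−q)(1−phi).

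With f = 1:

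| q | phi = 0 | phi = 0.5 | phi = 0.8 |
|---|---|---|---|
| 10% | 19.0% | 14.5% | 11.8% |
| 30% | 51.0% | 40.5% | 34.2% |
| 50% | 75.0% | 62.5% | 55.0% |

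At q = 30% the excess in subjects is:

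- phi = 0: 118 × 0.21 = 24.8
- phi = 0.5: 118 × 0.105 = 12.4
- phi = 0.8: 118 × 0.042 = 5.0

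With f = 0.5 these halve to 12.4, 6.2 and 2.5. With f = 0 (separate fields, device field used) or phi = 1 the excess is zero.

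A second form lets the two rates differ. Let pR be the share of subjects with a truly Radiesse-related event and pS the share with a Restylane-side procedure event. Under independence the excess is pS(1−pR). For pR = 30% and pS = 10% it is 0.10 × 0.70 = 7.0 points, or 118 × 0.07 = 8.3 subjects. For 30% and 30% it is again 21.0 points; without assuming independence it could lie anywhere from max(0, 0.30 − 0.30) = 0 to min(0.30, 0.70) = 30 points.

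The large values need a merged field, nearly every Restylane-side event flagged on an item that names the other device, and little correlation between two sides of one face injected under the same protocol.

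**The case for a change.** The best case for a change is that the asymmetry is on the page and is cheap to remove. Protocol 12.1.4 read with 12.3 lets a procedure-only event become an adverse device effect of the investigational device. Even with two fields, the visible SAP text does not say which one selects events for the endpoint, or which column is the headline figure. Separate items and one sentence in SAP 6.2.2 would add no patients and no visits.

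The uneven wording does stand, and so does the point that a merged field would mix device and procedure effects within the Radiesse column. Neither carries far:

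- The mixing would change little, because 12.1.4 counts an event as related whenever a link cannot be ruled out. For a reaction at a site just filled with Radiesse, the device question would often be answered yes in any case.
- The endpoint names Radiesse, so an analyst with separate device and procedure fields would use the device field.
- No headline column needs naming for a descriptive table that shows the treatment columns and the total together.
- Text is blacked out directly after the table sentence in SAP 6.2.2, so silence in the public version is weak evidence that the plan lacks a rule.

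**Conclusion.** No change to the plan follows. This is a gap in wording that those who build the form and program the table can be expected to fill sensibly. The feared error requires reading one bullet as one field, which the same list does not support. If that reading were right, the Radiesse column would still gain no Restylane-confined events. What could be over-counted is chiefly the total column of a descriptive secondary table, together with the Restylane and outside-area columns where the events would be visible.

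Any over-count would overstate Radiesse-related events. That is the same direction as the rule in Protocol 13.4.2 that treats missing causality as related, so it cannot hide a Radiesse risk. Tables of events regardless of relationship, which give the fair side-by-side comparison, do not use the causality items. The non-inferiority test, its type I error and the sample size are untouched.

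The size cannot be derived from the documents. Under the assumptions shown it runs from zero to about 25 of 118 subjects at a 30% event rate per side, and it is zero if device and procedure are recorded separately and the device item defines the endpoint. The conclusion rests on the location rule in SAP 6.2 being applied as written. It does not depend on the assumed rates.

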### **12.1.3 Severity Grading for an AE**

The clinical severity (i.e., intensity) of an AE will be classified as:

- Mild:** Signs and symptoms that can be easily tolerated. Symptoms can be ignored and disappear when the subject is distracted.
- Moderate:** Signs and symptoms that cause discomfort and interfere with normal functioning but are tolerable. They cannot be ignored and do not disappear when the subject is distracted.
- Severe:** Signs and symptoms that affect usual daily activity and incapacitate the subject, thereby interrupting daily activities.

The investigator is required to grade the severity (i.e., intensity) of each AE.

### **12.1.4 Causal Relationship of an AE with an Investigational Medical Device**

An AE is considered to be "related" to IMD or to the treatment procedure if a causal relationship between the IMD or the treatment procedure and an AE is at least reasonably

possible (i.e., the relationship cannot be ruled out). In this case, the non-serious event is considered an “adverse device effect” (Section 12.3). If the event is serious, it is a “serious adverse device effect” (Section 12.4).

The expression “reasonable causal relationship” is meant to convey that there are facts (evidence) or arguments to suggest a causal relationship. Otherwise, the relationship should be considered as “not related”.

### **12.1.5 Outcome Categories for an AE**

Reportable outcomes and/or sequelae of an AE may include the following:

- Recovered/resolved;
- Recovering/resolving;
- Not recovered/not resolved;
- Recovered/resolved with sequelae;
- Fatal; or
- Unknown.

If there is more than one AE, only the AE leading to death will be attributed with a “fatal” outcome.

## **12.2 Definition of a Serious Adverse Event (SAE)**

An SAE is an adverse event that:

- a) led to death;
- b) led to serious deterioration in the health of the subject, that either resulted in:
  - 1) a life-threatening illness or injury, or
  - 2) a permanent impairment of a body structure or a body function including chronic diseases, or
  - 3) inpatient or prolonged hospitalization, or
  - 4) medical or surgical intervention to prevent life-threatening illness or injury or permanent impairment to a body structure or a body function.
- c) led to fetal distress, fetal death, or a congenital abnormality or birth defect.

Note: Planned hospitalization for a pre-existing condition, or a procedure required by the CTP, without serious deterioration in health, is not considered an SAE.

### **12.2.1 Details of an SAE**

In cases of fatality, the cause of death is considered the AE, and the death is considered its outcome. In this case, the primary cause of death (i.e., the event leading to death) should be recorded and reported as an SAE. “Death” will be recorded as the outcome of this respective event; death will not be recorded as a separate event. Only if no cause of death can be reported (e.g., sudden death, unexplained death), the death *per se* might be reported as an SAE. In cases of death, an autopsy report should be submitted (if available). The date and cause of death should be recorded.

Planned hospitalization for a pre-existing condition is not considered an SAE. If a subject experiences an additional AE that prolongs a pre-planned hospitalization, this event is considered an SAE and should be reported as such. Hospitalizations for elective treatments planned before screening and which are documented in the subject’s source data are usually not regarded as SAEs.

In addition, device deficiencies, as defined in [Section 12.5](#), that might have led to an SAE if:

- a) suitable action had not been taken; or
- b) intervention had not been made; or
- c) if circumstances had been less fortunate

should be categorized as an SAE and reported accordingly.

### **12.2.2 Reporting and Handling of an SAE**

All SAEs that occur during the clinical trial period, whether considered to be related to the IMD or not, must be reported via fax, phone, or e-mail, and an SAE Report Form should be submitted to the sponsor and the CRO immediately upon knowledge of the event. The investigator will report the SAE to the clinical trial management departments of the clinical trial institution and the CRO. Further reporting details will be outlined in the Safety Management Plan.

Although all information required for completion of an SAE Report Form may not be available within the specified time period, an initial report should be submitted if the following minimal information is available:

- An identifiable subject (unique subject number);
- A suspect product and how the treatment relates to the SAE;
- An identifiable reporting source (investigator/investigative site identification); and/or
- An event or outcome that can be identified as serious.

The investigator must report SAEs to the sponsor and the CRO, as defined in [Section 12.2](#) and in compliance with Chinese GCP (Article 71), and to the site’s IEC/IRB, through the medical device clinical trial management department, per their reporting guidelines.

The sponsor’s Global Product Safety department will conduct an evaluation of the SAE and report the results of such evaluation to the CRO, who will, on behalf of the sponsor, report to regulatory agencies, IECs/IRBs through the medical device clinical trial management department, and investigators.

The investigator must supply further supporting information, and a detailed SAE description is an integral part of this supporting information. Follow-up SAE reports should be sent without delay to the sponsor and the CRO as an SAE Report Form (marked as a “follow-up” report), and the eCRF has to be updated accordingly to avoid discrepancies. The SAE has to be followed until the SAE is resolved/recovered or a plausible explanation is available. The SAE will be followed-up only in the Global Product Safety database after final SAE reconciliation is completed.

An SAE occurring after the end of the observational period would need to be reported if the investigator considers the event to be related to IMD. These reports generally will not be entered into the investigation database. Following database close for the trial, any ongoing SAEs will be followed until resolution or stabilization under the responsibility of the investigator per standard of care.

The investigator should complete and send any SAE Report Forms (including any follow-up forms) to the following contacts:

MERZ	CRO
Merz Pharmaceuticals GmbH Global Product Safety Department – Merz Aesthetics [name]	

### 12.3 Definition of an Adverse Device Effect (ADE)

An ADE is defined as an adverse event related to the use of an IMD.

Note:

1. This definition includes AEs resulting from insufficient or inadequate instructions for use, deployment, implantation, installation, or operation or any malfunction of the IMD.

2. This definition includes any event resulting from use error or from intentional misuse of the IMD.

## **12.4 Definition of a Serious Adverse Device Effect (SADE)**

An SADE is defined as an adverse device effect that has resulted in any of the consequences characteristic of an SAE ([Section 12.2](#)).

### **12.4.1 Definition of an Anticipated Serious Adverse Device Effect (ASADE)**

An ASADE is a serious adverse device effect which, by its nature, incidence, severity, or outcome, has been identified in the current version of the risk-analysis report.

### **12.4.2 Definition of an Unanticipated Serious Adverse Device Effect (USADE)**

A USADE is defined as follows:

- Any serious adverse effect on health or safety or any life-threatening problem or death caused by, or associated with, a device, if that effect, problem, or death was not previously identified in nature, severity, or degree of incidence in the investigational plan or application (including a supplementary plan or application), risk-analysis report, or IFU.
- Any other unanticipated serious problem associated with a device that relates to the rights, safety, or welfare of subjects.

